4.3.4 Missing Data

Missing data will not be imputed for the purpose of this analysis. All data recorded on the electronic case report form (eCRF) will be included in data listings that will accompany the clinical study report, as applicable. For qualitative parameters, a category with the number of patients with missing values will be presented where applicable.

Missing data imputations for Adverse Events will be included in the TEAE. Instead, the data will be presented in the AE listings.

4.3.5 Handling of Early Termination Visit Information

If a subject is terminated early from this study, the early termination visit data will be analyzed at the closest scheduled visit. If the closest visit has valid data, the early termination data will be assigned to the next available visit.

4.36 Pooling of Investigational Sites

The data from all study centers will be pooled together for all planned analyses.

Axiom Fusion eClinical Suite™Configured for the PTI-125-02 StudyPage 14 of 22

4.3.7 Coding Conventions for Events, Medical History and Medications

All adverse events and medical history indication will be mapped to the Medical Dictionary for Regulatory Activities (MedDRA) (version 22.1)

All Concomitant medications will be coded using World Health Organization (WHO) Drug Global C3 (version Mar 1, 2019).

4.3.8 Analysis Software

Data processing, tabulation of descriptive statistics, calculation of inferential statistics, and graphical representations will be performed primarily using SAS 9.4 for Windows. PK parameter C_{min} will be calculated using Phoenix WinNonLin. If the use of other software is warranted, the final clinical study report will detail what software was used and for what purposes.

4.3.9 Study Data

Study data identified in the schedule for time and events (Table 1) are collected, and source verified, on the electronic data capture tool: Axiom Fusion eClinical Suite (Axiom, Toronto, ON, Canada). The CANTAB cognitive test results will be provided to Axiom Biostats post unblinding of the database in comma-separated values (CSV) format.

All study data will be formulated into regulatory compliant data sets to provide transparency, traceability, and integrity of trial analysis results from the collection source. Observed study data will be mapped to the CDISC Study Data Tabulation Model (SDTM) and serve as the source data from the trial. All study analyses will be completed using analysis data sets that are derived from the SDTM and follow the CDISC Analysis Data Model (ADaM) architecture. All planned analyses will be performed using the ADaM data sets developed for this study.

The following Implementation Guides will be referenced for the configuration of SDTM and ADaM datasets:

- SDTM Model 1.4 and SDTM Implementation Guide (SDTM IG) version 3.2 will be used.
- ADaM Model 2.1 and ADaM Implementation Guide (ADaM IG) version 1.1 will be used.

Dropouts may be replaced during the study, will be included in the data analysis to the extent that evaluable data is present.

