7.2.3. Study Day 1 (Dosing Initiation)

Patients will come to the clinic in the morning. Prior to dosing, the following assessments will be conducted:

- Confirmation of inclusion/exclusion criteria
- Review of concomitant medications
- Vital signs (blood pressure, temperature, pulse and respiratory rate).
- Listen to heart and lungs
- Cambridge Cognition testing; the average of this result and that of the second screening visit will be taken as the baseline value.
- Blood sample collection for clinical laboratory tests
- Blood sample collection for PTI-125Dx and mTOR assessments (8 mL total)
- ECG

Patients will be administered Study Drug at least 1 h before or after a meal. The patient will be discharged 2 h later with their supply of Study Drug.

After dose on Study Day 1, the following assessments will be conducted:

- Vital signs (blood pressure, temperature, pulse and respiratory rate) at approximately 30 min, and 1 and 2 h post-dose.
- Adverse event monitoring

Clinic personnel will monitor the patients for the occurrence of any adverse events until patients are discharged from the clinic. Upon investigator judgment, patients will be discharged from the clinic with their supply of study drug until the next visit. The caregiver will be instructed to administer study drug twice daily at least 1 h before or after a meal. A dose can be up to 4 h late, but if a dose is missed, the next dose should NOT be doubled.

For all follow-up visits, patients will come to the clinic in the morning and will be instructed not to take their morning dose prior to coming to the clinic.

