10. STATISTICAL CONSIDERATIONS

10.1. RANDOMIZATION

Randomized treatments will be assigned by patient numbers in a randomly generated numeric sequence.

The randomization code will not be revealed to study patients, investigators, clinical staff or study monitors until all patients have completed therapy and the database has been finalized and locked.

Under normal circumstances, the blind should not be broken. The blind may be broken only if specific emergency treatment is indicated. The date, time and reason for the unblinding must be documented on the case report form, and the medical monitor must be informed as soon as possible.

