This SAP includes details of data handling procedures and statistical methodology. The final statistical analysis will proceed in accordance with this SAP as approved by both Cassava Sciences, Inc. and Axiom Real-Time Metrics. Any deviation from this SAP will be documented in the final Clinical Study Report (CSR). Any deviations from methods described in the protocol are also detailed and explained in this SAP.

The SAP will be finalized and approved prior to unblinding of any study data. Statistical programming of study data will be initiated as study data accumulates to ensure analysis program are setup and readily available prior to statistical delivery. Arbitrary treatment group assignments must be randomly linked to subjects, effectively rendering any output of programs meaningless.

For the reasons stated here the conduct of the study in the field is considered to be independent of any study outcome that might materialize upon enactment of the currently proposed statistical plan.

1. Study Objectives/Hypothesis Testing

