1.1 Study Objectives

Live v1.2 12Feb2020

The primary objectives for this study are to:

- Assess the safety of PTI-125 following 1-month, repeat-dose oral administration in mild-to-moderate Alzheimer's Disease (AD) patients, 50-85 years of age, with 16 ≤ MMSE ≤ 26.
- Assess the effect on biomarkers of PTI-125 following 1-month, repeat-dose oral administration in mild-tomoderate AD patients, 50-85 years of age, with 16 ≤ MMSE ≤ 26.
- Assess the effect on cognition of PTI-125 following 1-month, repeat-dose oral administration in mild-tomoderate AD patients, 50-85 years of age, with 16 ≤ MMSE ≤ 26.

The second objective is to replicate the effects on biomarker shown in the previous open label 1-month study.

The third objective is to investigate a dose response of PTI-125.

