1.2.2 Secondary Endpoint

- The secondary endpoint for this study will be to evaluate the change in CSF biomarkers from the second screening to Day 28 within the study treatment groups.
- The secondary endpoint for this study will be to evaluate the change in Cambridge Cognition testing from the Day 1 to Day 28 between each dose group and placebo
- ٩
- The secondary endpoint for this study will be the dose-response of the study drug.

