6.1 Efficacy Endpoints

The efficacy endpoints are summarized in Table 2.

Table 2. Summary of Efficacy Parameters

Parameter	Method of Determination / Derivation
Primary Efficacy Endpoint	
Change from Screening Visit 2 of the specific CSF biomarker on Day 28	Change = Day 28 – Screening Visit 2
The Cambridge Cognition tests results	NA

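### The cognition data reach the statisticians only after unblinding, with no CANTAB score named and the protocol's averaged baseline replaced, unexplained, by Day 1

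*SAP*

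**What the plan says.** **Timing.** SAP 4.3.9 says that "The CANTAB cognitive test results will be provided to Axiom Biostats post unblinding of the database", as a CSV file. The same section says that "Study data identified in the schedule for time and events (Table 1) are collected, and source verified, on the electronic data capture tool". Table 1 includes Cambridge Cognition testing, so the two sentences sit uneasily together. Protocol 10.1 withholds the randomisation code "until all patients have completed therapy and the database has been finalized and locked". Neither document describes a separate lock for the CANTAB file.

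**Endpoint.** One of the SAP's primary objectives (SAP 1.1) is to "Assess the effect on cognition of PTI-125 following 1-month, repeat-dose oral administration". SAP 1.2.2 makes cognition a secondary endpoint: "evaluate the change in Cambridge Cognition testing from the Day 1 to Day 28 between each dose group and placebo". SAP 6.2.2 analyses it as secondary, and Protocol 10.4 says the study is not powered for it. SAP Table 2 lists "The Cambridge Cognition tests results" with NA as the derivation. No test, score or composite is tied to the endpoint in either document.

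**Baseline.** Protocol 7.2.3 says of the Day 1 test that "the average of this result and that of the second screening visit will be taken as the baseline value". SAP 1.2.2 and 3.0 use Day 1. SAP 4.3.2 takes the last non-missing value up to the first treatment date, which is Day 1 when Day 1 is present. The SAP Introduction undertakes to explain departures from protocol methods, but this one is not explained.

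**Analysis.** SAP 6.2.2 specifies an ANCOVA of change with treatment and baseline. SAP 4.4.1 calls two-sided p ≤ 0.05 significant and states no adjustment across doses or scores.

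**The concern.** The SAP's protections against data-driven choices rely on decisions being made before the arms are known. Its Introduction has programs built on accumulating data under dummy treatment assignments, and section 8.0 foresees a review of blinded data. Neither can reach a file that the statisticians do not yet hold.

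That would matter little if the cognition analysis were fully fixed on paper, but it is not. The score is unnamed. SAP 4.1.1 requires evaluable efficacy records without defining evaluable, so which test sessions count is also open. Both can be settled after the code is open without departing from any written rule. With no score specified, whichever one is reported can be presented as the planned analysis, so the SAP's commitment to label post-hoc work gives no protection here.

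At stake is the credibility of the between-arm cognition result. A nominally significant finding could not be told apart from the best of several.

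**Working it through.** **The plan's own figure.** There is none to reproduce. Protocol 10.6 and SAP 2.6 give 60 patients without an effect size, SD, power or dropout rate. The only stated error rate is 0.05 two-sided per test.

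**Inputs from the documents:** 60 patients randomised 1:1:1, so 20 per arm (SAP 2.3.1); two dose–placebo comparisons (SAP 1.2.2); ANCOVA of change on treatment and baseline (SAP 6.2.2); 0.05 two-sided (SAP 4.4.1); Day 1 baseline (SAP 1.2.2, 3.0).

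**Assumed, because the documents do not say:** 3 or 6 candidate scores; correlation between scores 0.3 to 0.6; within-patient correlation between visits 0.7; no drug effect.

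**Step 1: hand calculation, treating all tests as independent.** With k scores and 2 doses there are 2k tests. A significant result in either direction has chance 1 − 0.95^(2k). One favouring drug has chance 1 − 0.975^(2k).

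| Scores | Either direction | Favouring drug |
|---|---|---|
| 1 | 1 − 0.95² = 0.098 | 1 − 0.975² = 0.049 |
| 3 | 1 − 0.95⁶ = 0.265 | 1 − 0.975⁶ = 0.141 |
| 6 | 1 − 0.95¹² = 0.460 | 1 − 0.975¹² = 0.262 |

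The shared placebo arm and positively correlated scores bring these down.

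**Step 2: simulation of the SAP's ANCOVA under the null.** Each patient's score at each visit is a stable part plus visit noise, and both parts are correlated across scores. The most favourable of the k scores over both doses is taken, always with the Day 1 baseline.

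| Scores | Either direction | Favouring drug |
|---|---|---|
| 1 | about 9% | about 5% |
| 3 | 21–25% | 11–13% |
| 6 | 31–40% | 16–20% |

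A repeat with 20,000 trials per setting gave 20.3–23.5% and 10.4–12.2% for 3 scores, and 31.3–39.9% and 16.0–20.7% for 6. The table is therefore good to about one percentage point. The range within a cell comes mainly from the between-score correlation: the higher it is, the smaller the inflation.

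**Step 3: what the averaged baseline is worth.** Take unit variance at each visit and correlation ρ between any two visits.

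- Residual variance with the Day 1 baseline: 1 − ρ².
- The average of two visits has variance (1 + ρ)/2 and covariance ρ with Day 28, so its residual variance is 1 − 2ρ²/(1 + ρ).
- At ρ = 0.6: 0.640 against 1 − 0.72/1.6 = 0.550, and 0.550/0.640 = 0.859, a reduction of about 14%.
- At ρ = 0.8: 0.360 against 1 − 1.28/1.8 = 0.289, and 0.289/0.360 = 0.802, a reduction of about 20%.

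The protocol's baseline is thus also the more precise one, and its data are already collected.

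**The case against.** The strongest reply is that SAP 4.3.9 fixes only when a file arrives. It does not say when sessions are reviewed or the score chosen, or by whom; the vendor might freeze the file beforehand. The SAP fixes the model, timepoints, analysis set and alpha, has covariates and subgroups identified before unblinding, and sends deviations to the study report. Its wording is compatible with reporting every score, in which case the issue would be unadjusted multiplicity. The table shells, a separate document not among those reviewed, may list the scores. Much of this stands: the documents show an open door, not a selection step. It does not close the door, because no lock is described and SAP 8.0 lets variable names in the shells change after data analyses.

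A reader might also infer four stronger things that the documents do not support:

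- **That the late transfer breaches the SAP's own rule.** The rule is that "The SAP will be finalized and approved prior to unblinding of any study data". A SAP approved in time and a file delivered later satisfy it.
- **That the baseline is a free choice.** Within the SAP it is consistently Day 1. Switching afterwards would be a deviation to be documented. Even free switching, for one score and one dose, moves 5% only to 6.4–7.6%. The defect is an unexplained departure from the protocol.
- **That cognition is a primary endpoint.** It is a primary objective, and its Table 2 row falls under the only visible sub-heading, the primary one. But SAP 1.2.2 and 6.2.2 make it secondary, and a sub-heading may have been lost when the table was extracted.
- **That the 21–40% rates measure bias towards the drug.** They count results in both directions; the drug-favouring rates are about half.

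**Conclusion.** The concern holds as an opportunity for selection: late transfer, an unnamed score and undefined session validity together allow the cognition result to be settled with the arms known. Nothing in the documents shows that this happened.

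The null chance of a nominally significant drug-favouring result rises from about 5% to about 11–13% (best of 3 scores) or 16–20% (best of 6), roughly a two- to four-fold increase. The numbers of scores and the correlations are assumptions. The calculation measures the effect of the unnamed score; the transfer time is what lets that choice be made unblinded, and is not itself modelled. The baseline departure is a separate, smaller matter of consistency and precision.

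Because cognition is a secondary, unpowered endpoint, this should be fixed but does not undermine the trial's primary biomarker analysis.

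**What to change.** 1. **SAP 4.3.9:** have the CANTAB file transferred, checked and locked before the randomisation code is released, and reconcile this with the sentence on electronic data capture.
2. **SAP 1.2.2 and Table 2:** before that lock, name one CANTAB score as the cognition endpoint, replace NA with its derivation and direction of benefit, and label the other scores exploratory. State the rule for an invalid session.
3. **SAP 1.2.2, 3.0 and 4.3.2:** use the protocol's average of Screening Visit 2 and Day 1 as the cognition baseline, and say what is done when one of the two is missing.

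The cost is SAP wording and an earlier vendor transfer; database lock may be a few days later. No new data are needed. With one score and one baseline fixed, the chance of a nominal finding in either direction over the two doses is still about 9%. That comes from testing two doses unadjusted, which is a separate question.

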4.4 Planned Analyses

4.4.1 Statistical Summaries: Descriptive and Inferential

All statistical tests will be two-sided and a difference resulting in a p-value of less than or equal to 0.05 will be considered statistically significant.

All p-values will be rounded to and displayed in four decimals. If a p-value less than 0.0001 occurs, it will be shown in tables as <0.0001.

Descriptive summaries of variables will be provided where appropriate. For continuous variables, the number of nonmissing values (n) and the median, mean, standard deviation, minimum, and maximum will be tabulated by treatment. For categorical variables, the counts and proportions of each value will be tabulated by treatment.

Data will be presented as listings where applicable. Data not subject to analysis according to this plan will not appear in any tables or graphs but will be included in the data listings.

5.0 Summary of Baseline Characteristic Data

5.1 Subject Disposition

Subject disposition will be summarized by treatment and will include:

- The number of subjects randomized
- The number of subjects in the FAS set
- The number of subjects in the safety set
- The number and percentage of subjects who completed or discontinued the study at each study site (based on actual treatment, not randomization)

All percentages will be based on the number of subjects randomized. A subject level data listing of study completion information including the reason for premature study withdrawal, if applicable, will be presented.

5.2 Protocol Deviations

All protocol violations will be captured directly in Fusion and they will be presented in a data listing.

5.3 Demographics and Baseline Characteristics

The demographics consist of age (year), sex, race, and ethnicity. The baseline characteristics consist of baseline height (cm), baseline weight (kg), and baseline body mass index (BMI) (kg/m2). Body mass index is calculated as (body weight in kilograms) / (height in meters)2.

Subject demographic data and baseline characteristics will be tabulated and summarized descriptively by treatment group. The demographic data and baseline characteristics will be summarized for the FAS population.

Individual subject demographics and baseline characteristics will be provided in listings.

5.4 Medical Histories

Medical history will be coded using Medical Dictionary for Regulatory Activities (MedDRA) (Version 22.1). Subject medical history data including specific details will be presented in a listing.

Axiom Fusion eClinical Suite™Configured for the PTI-125-02 StudyPage 16 of 22

5.5 Concomitant Medications

Concomitant medications will be coded using World Health Organization Drug Dictionary (WHO-DD) Global C3 (Version Mar 1, 2019).

All medication data will be presented in listings;

5.6 Treatment Compliance

Study medication compliance will be calculated based on the numbers of tablets dispensed minus the number of tablets returned divided by the expected number of tablets based on the duration of the subject's participation in the study.

- Treatment compliance will be summarized by treatment group.
- Treatment compliance data will be presented in a data listing.

6.0 Efficacy Analysis

All the efficacy analyses will be performed using the FAS population.

6.1 Efficacy Endpoints

The efficacy endpoints are summarized in Table 2.

Table 2. Summary of Efficacy Parameters

Parameter	Method of Determination / Derivation
Primary Efficacy Endpoint	
Change from Screening Visit 2 of the specific CSF biomarker on Day 28	Change = Day 28 – Screening Visit 2
The Cambridge Cognition tests results	NA

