| Percent Change | -32.1% | -21.5% | -19.8% | -34.4% | 4.3% | -9.4% | -14.3% | -11.1% | -5.1% |
| P value* | p < 0.00001 | p < 0.00001 | p < 0.00001 | p < 0.00001 | N.S. | p = 0.043 | p < 0.00001 | p < 0.00001 | p < 0.001 |

*Screening vs. Day 28, paired t test

Fig. 1 Mean Change from Baseline to Day 28 in CSF biomarkers (±SEM)

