3. STUDY OBJECTIVES

The objectives of this study are to investigate the safety and effect on biomarkers and cognition of PTI-125 following 1-month, repeat-dose oral administration in mild-to-moderate AD patients, 50-85 years of age, with MMSE \geq 16 and \leq 26. A second objective is to replicate the effects on biomarkers shown in the previous open-label 1-month study (PTI-125-03). A third objective is to investigate a dose-response of PTI-125.

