6.2 Efficacy Analyses

6.2.1 Primary Efficacy Analysis

CSF Biomarkers

The baseline, post baseline, and change from baseline values will be summarized by treatment group based on the FAS population. The change from baseline on Day 28 will be analyzed by using a General Linear Model for the ANCOVA. The model will include the change from baseline as the dependent variable, the fixed effect of treatments, and baseline CSF biomarkers measurement as covariate. The means, Least Squares (LS) means, a 2 sided 95% confidence intervals (CI) for each LS means, differences between LS means, a 2 sided 95% CIs for each difference and the p-values from model effects will be reported in the summary table.

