6.2.2 Secondary Efficacy Analysis

CSF Biomarkers at Screening Visit 2 and Day 28 will be compared by using the two tailed paired t-test per each treatment group (Placebo, PTI-125 50 mg, and PTI-125 100 mg). The analysis will be performed based on the FAS population. The means, differences between means of Screening Visit 2 and Day 28, a 2 sided 95% CIs for the difference and the p-values from the t-test will be reported in the summary table.

Cambridge Cognition Test

Results will be summarized for subjects by treatment group. The summary and statistical analysis will be conducted using FAS population. The change from baseline on Day 28 will be analyzed by using a General Linear Model for the ANCOVA. The model will include the change from baseline as the dependent variable, the fixed effect of treatments, and baseline Cambridge cognition measurement as covariate. The means, Least Squares (LS) means, a 2 sided 95% confidence intervals (CI) for each LS means, differences between LS means, a 2 sided 95% CIs for each difference and the p-values from model effects will be reported in the summary table.

Dose Response Analysis 6.2.3

Nonlinear Emax model will be used in dose-response analysis. The model has the following form:

$$R_i = E_0 + \frac{D_i^N \times E_{max}}{D_i^N + ED_{50}^N} + \varepsilon_i$$

Where:

i = patient;

 R_i = The value of response for patient i (ex. Defined to be "Change form Baseline in A β_{42} at Day 28" should be repeated for the remaining CSF Biomarkers);

 D_i = Concentration of the drug in the plasma of the patient *i* at Day 28;

 E_0 = Basal response, when the concentration of the drug is zero or minimal;

 E_{max} = The maximum response attributable to the drug;

ED₅₀ = The concentration that produces half of maximum response;

N = The slope measures the change in response by moving from one concentration level to another;

 ε_i = The random error term for patient *i* – i.i.d and follows normal distribution with mean – 0 and variance.

Treatment group response will be predicted by applying the Emax model which intrinsically has 4 parameters to estimate (E0, Emax, ED50, N). This can be performed with "Proc NLIN" procedure in SAS by arbitrary specifying starting estimates for these parameters by treatment groups.

To assure optimal convergence of the procedure, the following starting estimates will be applied:

	Placebo	PTI-125 50mg	PTI-125 100mg
E ₀	0	Minimum response from observed data	Minimum response from observed data

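### Does the SAP need a prespecified percent-change estimate for the CSF biomarkers, because the earlier study's effects are given as percents?

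*SAP*

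**What the plan says.** SAP 6.1, Table 2, sets the CSF endpoint as an arithmetic difference: "Change = Day 28 – Screening Visit 2". SAP 6.2.1 carries it into the primary analysis as follows: "The model will include the change from baseline as the dependent variable, the fixed effect of treatments, and baseline CSF biomarkers measurement as covariate". That section also summarises baseline, Day 28 and change values by arm, and SAP 4.4.1 says that such summaries give n, mean and SD.

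SAP 6.2.2 adds a two-tailed paired t-test within each arm, placebo included, and reports: "The means, differences between means of Screening Visit 2 and Day 28, a 2 sided 95% CIs for the difference and the p-values". The Emax model in SAP 6.2.3 also takes change from baseline as its response. The SAP text specifies no percent, ratio or log-scale CSF estimate.

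On replication, SAP 1.1 says: "The second objective is to replicate the effects on biomarker shown in the previous open label 1-month study". Protocol section 3 says the same. The results to be replicated are in protocol section 2, Table 5, in a row labelled "Percent Change", with p-values footnoted "Screening vs. Day 28, paired t test". Table 5 gives no raw changes, SDs or confidence intervals, and the protocol states neither the percent formula nor the size of that study.

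**The concern.** A reader who wants to know whether the effects were replicated will set this trial's percent change beside Table 5. The SAP does not define that percent, so it would be calculated outside the prespecified analyses, perhaps after unblinding.

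There are at least three candidates: the percent change of the arm means, the geometric mean ratio, and the mean of the patients' individual percent changes. They need not agree. If they differed by as much as the smaller Table 5 effects (TNF-alpha -5.1%, YKL40 -9.4%), the choice of formula could decide whether the earlier result seemed to be reproduced.

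**Working it through.** **1. Can a percent be obtained from what is planned?** For each arm, SAP 6.2.1 with 4.4.1 gives n, mean and SD at Screening Visit 2 (X), at Day 28 (Y) and for the change (D). SAP 3.0 limits the biomarker analysis to patients with both samples, so the three sets of figures describe the same patients. Then:

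- percent change of means = 100 × (mean Y / mean X - 1);
- Cov(X,Y) = (SD_X² + SD_Y² - SD_D²) / 2;
- with r = mean Y / mean X, SE(r) = sqrt[(SD_Y² + r² SD_X² - 2r Cov) / n] / mean X.

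In simulations with 20 patients per arm, 95% intervals built this way covered 92.8% to 95.8%. The raw interval alone does not convert to a percent interval, but the planned tables contain what is needed.

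**2. How far apart are the formulas?** Take multiplicative visit error with mean 1 and a within-patient coefficient of variation (CV). The ratio of means and the geometric mean ratio both recover the true reduction. The mean of individual percents is shifted upwards by (1 - reduction) × CV². For a true -20%:

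- CV 15%: 0.80 × 0.0225 = 1.8 points, giving -18.2%;
- CV 25%: 0.80 × 0.0625 = 5.0 points, giving -15.0%.

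With additive error (SD 15% of the mean), the three formulas span about 3 points at a between-patient CV of 20%. They reach about 10 points only at a between-patient CV of 70%.

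The grouping also depends on the model. In a simulation with a geometric mean ratio of 0.656, log-ratio SD 0.25 and noise only at Day 28, the two arithmetic percents agreed at about -32.3% and the geometric one stood apart at -34.3%.

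**3. Which CVs are compatible with Table 5?** A paired t-test on log values with n patients has t = |ln(1 - reduction)| × sqrt(n) / (sqrt(2) × s), where s² = ln(1 + CV²). Solving for s at the critical t of the reported p-value gives an upper limit for the CV (for YKL40, reported as p = 0.043, the implied value). The documents do not give the earlier study's n, so a range is assumed.

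| Marker (Table 5) | CV, n=10 / 20 / 40 | Formula shift in points, n=10 / 20 / 40 |
|---|---|---|
| TNF-alpha -5.1%, p<0.001 | 2.4 / 4.3 / 6.6% | 0.1 / 0.2 / 0.4 |
| IL-1beta -11.1%, p<0.00001 | 3.0 / 6.3 / 10.4% | 0.1 / 0.4 / 1.0 |
| IL-6 -14.3%, p<0.00001 | 3.9 / 8.2 / 13.7% | 0.1 / 0.6 / 1.6 |
| YKL40 -9.4%, p=0.043 | 9.4 / 14.5 / 21.3% | 0.8 / 1.9 / 4.1 |
| pTau -34.4%, p<0.00001 | 10.7 / 22.7 / 38.5% | 0.8 / 3.4 / 9.7 |

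Example, TNF-alpha at n=20: |ln 0.949| = 0.0523 and t = 3.883, so s = 0.0523 × 4.472 / (1.414 × 3.883) = 0.0426. The shift is 0.949 × 0.0426² = 0.0017, or 0.2 points.

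At a CV of 15% (s = 0.149), the TNF-alpha p-value would need n = (3.35 × 1.414 × 0.149 / 0.0523)², about 182 patients. A CV of 15% to 25% is therefore not credible for this marker at a modest n.

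**4. Would an added interval settle replication?** Table 5 has no interval. If the true effects and variances were identical, a new 95% interval from 20 patients would contain the earlier point estimate only about 76% of the time (earlier n=10) or 85% (earlier n=20). The entry criteria differ as well: MMSE 16-24 and total tau/Aβ42 ≥ 0.30 in the earlier study (protocol section 2), against 16-26 and ≥ 0.28 here (protocol 5.2).

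**The case for a change.** The strongest case for a change is that replication is a stated objective, that Table 5 gives the size of the effects only as percents, and that naming a formula before unblinding costs a few sentences. The planned paired t-test covers direction and significance but not size on the published scale. The shift is also not negligible everywhere: if the earlier study had about 40 patients, the limits allow roughly 4 points for YKL40 and up to nearly 10 for pTau.

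The factual part stands: the SAP text names no percent estimate. The consequence does not. The objective is to replicate effects, and SAP 1.2.2 and 6.2.2 express that as within-arm change, tested as before and now with an interval and a placebo arm. Any further calculation is covered by the SAP's Purpose section, which requires post-hoc analyses to be clearly identified in the study report. For pTau, the loose limit at n=40 belongs to an effect of -34.4%, so a shift of that size would not hide it.

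A log-scale interval would not guarantee a like-for-like comparison, because Table 5's formula is unstated. It would also add 9 markers × (3 within-arm + 2 between-arm) = 45 unadjusted intervals. Finally, the display shells are in a separate mock-tables document (SAP 8.0) that could not be examined and may already contain a percent column.

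**Conclusion.** No change is needed. The planned raw-scale analyses are valid, their scale is fixed in the SAP, and the within-arm test matches the one behind Table 5. The missing percent is a reporting gap that an analyst can fill from the planned tables, and filling it alters no planned test or conclusion.

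With an earlier study of 10 to 20 patients, the formula would move the percent by at most about 0.6 points for TNF-alpha, IL-1beta and IL-6, and by about 1 to 3 points for YKL40 and pTau. These sizes assume multiplicative error, a paired test on log values and within-patient noise like that of the earlier study; none of this is stated in the documents. If the earlier test was on raw values under the same error model, spread in baseline levels would add to the variance of the changes, so the CV limits would if anything be tighter. A sponsor who wishes to help readers may print a descriptive percent change with its formula; that is optional.
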